4.7. Calculation of number of days and age

◇ Day

The number of days from the start date of this drug treatment will be calculated as follows in cases where the target day is before or after the start date of this drug treatment.

- In the case of the start date of this drug treatment \leq the target date: the target date - the start date of this drug treatment +1
- If the start date of administration of this drug $>$ target date: target date - start date of administration of this drug

*The number of days (Day) after the start of this drug administration is shown as 1 for the start day of this drug administration and -1 for the day before the start of this drug administration, with 0 not used.

◇ Age

Calculated using the start date of administration of this drug. However, if age data are separately obtained, the data will be preferentially adopted.

- this drug Start Date - Date of Birth (* Calculated with June 30 imputed.)

4.8. Drug Class

Drug Class	Definition
Immunosuppressants	To be defined in a separate document
Antimalarial drugs	
Steroids	
NSAIDs	
Biological preparations-Miscellaneous	
Cyclophosphamide IV	

4.9. Concomitant conditions

Concurrent medical conditions will be coded using MedDRA and tabulated according to the following categories.

Concomitant conditions	Definition
Hepatitis B	Same as the study plan
Renal impairment	HLGT (10029149): Nephropathy HLGT (10038430): Renal disorders (excl nephropathy)
Hepatic impairment	SMQ: PTs included in level 1 “Liver disorders (20000005)”, excluding PTs included in level 3 “Liver related coagulation and bleeding disorders (20000015)”
Allergy	HLGT (10001708): Allergic diseases
Other	Complications other than the above listed in the survey form

4.10. Responders

A responder is defined as a case where this drug treatment start date and post-treatment assessments are present and the following conditions are met:

Efficacy assessments	Responder definition
SELENA SLEDAI (Used for calculation of efficacy percentage)	≥ 4 decrease in score from baseline
PGA score	≥ 0.3 (10 mm) decrease from baseline
LLDAS (Lupus Low Disease Activity State)	1. SELENA-SLEDAI ≤ 4 and no major active organ involvement (renal, central nervous system, cardiopulmonary, vasculitis, pyrexia) on SELENA-SLEDAI, without hemolytic anemia or active gastrointestinal lesions reported as adverse events.
	2. No new signs or symptoms as compared to the last SELENA-SLEDAI assessment.
	3. PGA score ≤ 1 (33 mm)

Efficacy assessments	Responder definition
	4. Corticosteroid dose ≤ 7.5 mg/day at time of assessment
	5. Use of the same immunosuppressant as compared with prior medication. No unapproved drugs of rituximab, anifrolumab, ustekinumab, or baricitinib are used as concomitant medications. The use of anifrolumab with this drug initiated on 2021/9/27 or later is allowed.
LLDAS Adverse Events	Haemolytic anaemia: 10018916 (PT code) Active gastrointestinal lesions: to be defined in a separate document
Corticosteroid Reduction at Week 40~52	Average daily dose Proportion of patients who were able to reduce their average daily steroid dose by $\geq 25\%$ and ≤ 7.5 mg/day from baseline at Week 40~52 (in patients with baseline average daily steroid dose > 7.5 mg/day). Subjects who discontinued or completed administration of this drug before Week 52 will be classified as non-responders.

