4.4.4. Categorical data

- ✧ Data should be handled as "unknown" regardless of whether it is missing, unknown, or not recorded.
(Excluding those defined in 4.6. Handling of presence/absence)
- ✧ Unless otherwise specified, missing values will be included in the denominator of percentages.
- ✧ Odds ratio excludes unknown category.

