	
< Summary statistics >
 
 • Anti-dsDNA [IU/mL] • C3[mg/dL] • C4[mg/dL] • CH50[U/mL] • Protein-creatinine ratio [g/g • Cr]
Screening test	
< Category >
 
 • Tuberculosis Screening Prior to Initiation of this drug 
 Presence or absence of chest imaging, tuberculin test, and interferon-γ release assay (No, Yes) Chest imaging/presence or absence of tuberculosis (If absent or present, by active tuberculosis or old tuberculosis), including findings of old tuberculosis PPD skin test/positive status (Negative, Positive) Interferon-gamma release assay/positive status (Negative, Positive) • Hepatitis B screening prior to initiating this drug 
 Presence or absence of HBs antigen, HBs antibody, HBc antibody, and HBV-DNA quantification (No, Yes)

		HBs antigen/positive status (Negative, Positive)
		HBs Ab/positive status (Negative, Positive)
		HBc Ab/positive status (Negative, Positive)
		• Patients with special surveillance item (reactivation of hepatitis B virus)
		HBs antigen, HBs antibody, HBc antibody, and HBV-DNA assay in patients with priority investigation item (reactivation of hepatitis B virus) (Yes)
		< Summary statistics >
		• HBV-DNA, quantitative [Log IU/mL]
Proper status	use	< Category >
		• Prior medications for SLE (Steroids, immunosuppressants, antimalarials, NSAIDs, other biologics, cyclophosphamide intravenous injection)
		Prior treatment for SLE (No, Yes)
		SELENA SLEDAI score by presence/absence of prior treatment for SLE ($0 \leq$ to <4 , $4 \leq$ to <10 , $10 \leq$ to <12 , $12 \leq$, not judged)
		Prior medications for SLE (Steroids, immunosuppressants, antimalarials, NSAIDs, other biologics, cyclophosphamide intravenous injection)
		• Autoantibodies associated with SLE
		Antinuclear antibody or anti-dsDNA antibody (Positive (antinuclear antibody [positive] and/or anti-dsDNA [positive]), negative, or not done)
		SLE-related autoantibodies (antinuclear or anti-dsDNA [negative or not performed]): other autoantibodies (positive) (overlapping) (Anti-Smith, lupus anticoagulant, anticardiolipin, and other autoantibodies associated with SLE), negative for all or not performed

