6.4. EFFICACY EVALUATION

6.4.1. Response rate by patient characteristic (Tables 3.01 and 10.1)

Analyzed:	Efficacy analysis population
Analysis details:	
The number of target patients, number of effective/ineffective patients, and response rate will be calculated for each patient background item, initial administration route, and administration route.
 
The SELENA SLEDAI score will be used for the number of responders, number of non-responders, and response rate.
 
The denominator of the response rate is the number of patients included in each baseline characteristic.

Patient characteristics:	Same items as "Patient composition ratio," initial route of administration, route of administration

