6.4.2. Changes in responder rates (LOCF) (Tables 3.021, 3.0211, 3.0212, 3.022, 10.2)

Analyzed:	Efficacy analysis population
Analysis details:	
The number of responders/non-responders and the responder rate will be calculated in chronological order for each efficacy endpoint (SELENA SLEDAI score, PGA score, LLDAS, reduction of steroid dose at Week 40~52). 95% confidence intervals will be calculated for assessment at discontinuation/completion (LOCF).
 
Data will also be summarized by the presence or absence of severe lupus nephritis, presence or absence of severe central nervous system lupus, and route of administration as reasons for this drug use.
 
For data at discontinuation/completion (LOCF), the same analysis will be performed by patient characteristic.
 
For steroid dose reduction at Week 40~52, subjects whose baseline average daily steroid dose is > 7.5 mg/day will be included.

Chronological order:	Week 24, Week 52, at discontinuation/completion (LOCF), and Week 40~52 (steroid dose reduction at Week

40~52)

Patient characteristics:	
• SELENA SLEDAI (baseline): $\leq 9, \leq 10$• Anti-dsDNA antibody (baseline) [IU/mL]: $<30, 30 \leq$• Complement Levels:
Low C3 and/or Low C4Other than the above• C3 (baseline) [mg/dL] ($<90, 90 \leq$)• C4 (baseline) [mg/dL] ($<10, 10 \leq$)• Use of steroids at the start of treatment: No, Yes• Baseline steroid [mg/day]: $\leq 7.5, 7.5 <$• Immunosuppressant use: No, Yes
--------------------------	--

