6.4.3. Changes over time in efficacy endpoints (LOCF) (Tables 3.03, 3.0301, 3.0302)

Analyzed:	Efficacy analysis population
Analysis details:	
Summary statistics of (SELENA SLEDAI, PGA, Lupus Impact Tracker) will be calculated for each efficacy endpoint in chronological order.
 
Data will also be summarized by the presence or absence of severe lupus nephritis and by the presence or absence of severe central nervous system lupus as the reason for this drug use.

Calculation items:	Score, change, percent change
Chronological order:	Baseline, Week 24, and Week 52, and at discontinuation/completion (LOCF)

6.4.4. Change in the proportion of responders per system organ class in SELENA SLEDAI score (LOCF) (Tables 3.04, 3.0401, 3.0402)

Analyzed:	Efficacy analysis population
Analysis details:	
SELENA SLEDAI score The proportion of patients with a decrease in SELENA SLEDAI score from baseline will be calculated over time for each organ system index.
 
Data will also be summarized by the presence or absence of severe lupus nephritis and by the presence or absence of severe central nervous system lupus as the reason for this drug use.

CONDITION:	Patients with baseline SELENA SLEDAI score > 0 will be included.
Chronological order:	Week 24, Week 52, or at discontinuation/completion (LOCF)

6.4.5. Proportion of patients with worsening of SELENA SLEDAI score by organ system over time (LOCF) (Tables 3.05, 3.0501, 3.0502)

Analyzed:	Efficacy analysis population
Analysis details:	
SELENA SLEDA score The proportion of subjects with worsening of SELENA SLEDAI score from baseline will be calculated over time for each organ system index.

Data will also be summarized by the presence or absence of severe lupus nephritis and by the presence or absence of severe central nervous system lupus as the reason for this drug use.

CONDITION: Patients with baseline SELENA SLEDAI score ≥ 0 will be included.

Chronological order: Week 24, Week 52, or at discontinuation/completion (LOCF)

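### The SELENA SLEDAI response rate includes patients whose baseline score is too low to allow a response, which lowers the rate and biases comparisons against low-score subgroups

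*SAP*

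**What the plan says.** SAP 4.10 sets the SELENA SLEDAI response as a "≥ 4 decrease in score from baseline" and marks it as the measure used for the efficacy percentage. PGA response is a fall of at least 0.3.

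SAP 6.4.1 says: "The denominator of the response rate is the number of patients included in each baseline characteristic". SAP 6.4.2, which carries the 95% confidence interval, states no SELENA SLEDAI denominator. The defaults then apply: 5.2 divides by the number of patients analysed, and 4.4.4 adds "Unless otherwise specified, missing values will be included in the denominator of percentages". SAP 6.4.12 also divides by the number of patients.

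The survey takes all treated patients aged 15 or over, with no minimum score (Protocol section 3). The efficacy exclusions in SAP 4.3.2 are off-label use (an indication other than SLE, or paediatric use) and unspecified committee decisions. The proper-use rows of 6.2.1 tabulate "SELENA SLEDAI score by presence/absence of prior treatment for SLE", with a lowest class from 0 to below 4.

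For steroid reduction, by contrast, 6.4.2 sets a baseline condition: "subjects whose baseline average daily steroid dose is > 7.5 mg/day will be included". For organ-system improvement, 6.4.4 says: "Patients with baseline SELENA SLEDAI score > 0 will be included".

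**The concern.** A response rate is normally read as the chance of improving among patients who could improve. Here some patients count as non-responders because of where they started, whatever the drug does. The SAP avoids this for steroids by requiring a baseline dose above the target, but sets no such condition for SELENA SLEDAI or PGA.

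The SELENA SLEDAI rate feeds the tables by complication (6.2.2), prior drug (6.2.3), concomitant drug (6.2.4) and patient characteristic (6.4.1), the time course (6.4.2) and the steroid-category tables (6.7). The 6.4.2 subgroups include baseline SELENA SLEDAI, anti-dsDNA and complement, all of which are tied to the starting score. Protocol section 9 also plans odds ratios for factors that may affect effectiveness. A reader could take a difference created by the floor for a difference in drug effect.

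**Working it through.** The plan states no expected response rate, so there is no figure of its own to reproduce. The sample size (553, rounded up to a target of 600) rests on serious infections and is not affected.

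**1. The floor.** The lowest possible score is 0, so a patient's largest possible fall equals the baseline score. With baseline 0 to 3 the fall is at most 3, below the 4 required. Non-response is certain.

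**2. Reported rate.** Let R be the response rate among patients with baseline of 4 or more, and e the share with baseline below 4. Then

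reported rate = R × (1 − e) + 0 × e = R × (1 − e).

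**3. Baseline subgroup.** Section 6.2.1 splits baseline SELENA SLEDAI at 9 or less against 10 or more (6.4.2 prints the second class as ≤ 10, apparently a slip). Every patient below 4 falls in the lower class and none in the upper. With the same R in both classes, the upper class reports R and the lower class reports R(1 − e), where e is now the share within the lower class. The odds ratio for upper against lower is

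[R / (1 − R)] ÷ [R(1 − e) / (1 − R(1 − e))].

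R and e are not in the documents; the values below are assumed.

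| R | e | R(1 − e) | Odds ratio, ≥10 vs ≤9, with no real difference |
|---|---|---|---|
| 50% | 10% | 45% | 1.22 |
| 50% | 20% | 40% | 1.50 |
| 50% | 30% | 35% | 1.86 |
| 60% | 10% | 54% | 1.28 |
| 60% | 20% | 48% | 1.62 |
| 60% | 30% | 42% | 2.07 |

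**4. Complement and anti-dsDNA.** In SAP 4.11, low complement and anti-dsDNA score 2 points each. A patient scoring both has at least 4 points and is never below the floor. A patient scoring neither must reach 4 from other items. One therefore expects more patients below the floor where complement is normal or the antibody is negative. If two such groups had 10% and 30% below the floor and R = 50% in both, they would report 45% and 35%, an odds ratio of (0.45/0.55) ÷ (0.35/0.65) = 1.52. This direction is expected rather than certain, because the laboratory cut-offs in 6.4.2 need not match the scoring of the SELENA SLEDAI items.

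**5. PGA.** A fall of 0.3 is impossible from a baseline below 0.3. Section 6.2.1 tabulates a PGA class starting at 0, and no rule removes these patients.

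**6. Patients without a score.** SAP 4.10 says: "A responder is defined as a case where this drug treatment start date and post-treatment assessments are present". As worded, this limits who is a responder, not who is counted. SAP 4.4.4 keeps missing values in percentages, but 4.1 counts patients who meet applicable conditions, and 6.4.1 lists only effective and ineffective patients, with no unknown outcome. LOCF (4.4.2) helps only where some post-baseline value exists. SAP 4.4.4 also says "Odds ratio excludes unknown category"; if that covers an unknown response, odds ratios and percentages would have different denominators. Two programmers could reasonably produce different rates.

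**7. Organ systems.** Improvement in 6.4.4 requires a baseline score above 0; worsening in 6.4.5 requires a baseline score of 0 or more. Both are calculated for each organ system. The pairing makes sense at organ level, since an organ can improve only from above 0 but can worsen from 0. The text does not say which score is meant.

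**The case against.** Several points on the other side stand.

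- **Size.** The label excerpt in Protocol section 3 calls for disease activity, and the class from 0 to below 4 sits under proper use, so it may be only a check. Its presence does not show that such patients are common. Nothing indicates how many have PGA below 0.3.
- **Unassessed patients.** A reader might infer that patients never assessed are also in the denominator and wrongly depress the rate. The text is ambiguous on this, and counting them as non-responders is a recognised conservative convention. The steroid row in 4.10 does much the same for patients who stop before Week 52. Dropping them could inflate the rate.
- **Organ rates.** A reader might infer that 6.4.4 conditions on the total score, so that an organ involved in 10% of patients could never show more than 10% improvement. The pairing with 6.4.5 suggests that the organ's own score was meant.
- **Influencing factors.** A reader might infer that low-score factors will emerge as predictors of non-response in the formal analyses. SAP 5.4 and 6.6 are blacked out, so adjustment for baseline score cannot be judged. The point is limited to the visible descriptive tables.
- **Other outputs.** Section 6.4.3 summarises score, change and percent change, and LLDAS needs no 4-point fall. The survey is single-arm, and no response rate is tested against a threshold.
- **Residual dependence.** A baseline of at least 4 does not remove all dependence on baseline: from 4 a patient must reach 0, while from 12 a fall to 8 is enough.

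None of this answers the central point. Patients starting at 0 to 3 cannot respond, no written rule removes them, and all of them fall in the lower baseline stratum.

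**Conclusion.** The point holds for patients below the floor. If any patient has a baseline below 4, the all-patient SELENA SLEDAI rate is below the rate in patients able to respond, by the factor (1 − share below 4), and the comparison by baseline score is biased against the lower class. The bias by complement and anti-dsDNA is likely, through the 2 points each contributes. The same logic applies to PGA below 0.3.

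Only the direction follows from the documents. The figures in the working rest on assumed true rates of 50% or 60% and assumed shares of 10% to 30%; with few such patients the effect is small. The documents do not support calling the handling of unassessed patients an error, or saying that the organ rates are capped by organ prevalence. Both are matters of unclear wording. The survey's sample size does not depend on this point.

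**What to change.** - In SAP 4.10, 6.4.1 and 6.4.2, report the response rate in patients with baseline SELENA SLEDAI of at least 4 (PGA of at least 0.3) beside the all-patient rate, overall and by subgroup. Base subgroup comparisons on the restricted rate.
- For each response table, state the denominator and whether patients without a post-baseline score count as non-responders.
- Show the number below the floor and the number not assessed, overall and by subgroup.
- In 6.4.4, state that the above-0 condition refers to that organ domain's own baseline score.

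Keeping the all-patient rate preserves comparability with the interim outputs. The cost is SAP wording, a filter in the programs and extra table rows, with a smaller n in the restricted rows. No new data are needed.

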- ii) Number of patients included in the safety analysis set and number of patients included in the effectiveness analysis set, number of patients excluded from analysis and the reason for exclusion

2) Safety-related matters

- i) Occurrence of ADRs/infections (type, severity, and incidence rate of ADRs, etc.)
- ii) Factors that potentially affect safety (occurrence of ADRs and infections by patient characteristics, etc.)
- iii) Occurrence of ADRs of events defined as a priority study matter

3) Effectiveness-related matters

- i) Changes in SELENA SLEDAI score, Lupus Impact Tracker score, PGA score, steroid dose, each laboratory test item, and achievement of Lupus Low Disease Activity State (LLDAS)

2. Analysis methods

Concerning the items associated with safety and effectiveness, etc., the odds ratio and 95% confidence interval will be calculated for the factors that potentially affect them. These will be graphically presented using a forest plot, etc., as appropriate. For comparison of the scores, etc., the mean values and quartile points, etc. for values at the time of measurement and changes from baseline will be calculated.

10. Organizational Structure

See Attachment 1.

11. Name, Address of the Outsourcees, and the Scope of the Outsourced Operations

CCI

12. Scheduled Timing to Be a Milestone for Assessing the Status and Results in the Study or Reporting to the Pharmaceuticals and Medical Devices Agency (PMDA) and Rationale

- At the time of Periodic Safety Reports : consideration will be comprehensively given to the safety and effectiveness information.
- At the time of re-examination application : the final report will be prepared/submitted, based on the results of tabular analysis obtained from the fixed data of all collected CRFs.

13. Additional Measures that Have a Potential to Be Taken Depending to the Study Results and the Decision Criteria for the Start

The Risk Management Plan, including the following, will be reviewed at the timings to be a milestone.

- Regarding the safety specification, including the priority study matters, if the proportion of occurrence, peak occurrence period and risk factors become visible as an ADR caused by Benlysta, the necessity for revising the Package Insert and study materials will be considered as appropriate.
- Including whether or not a new concern in the safety specification is present, the necessity for changes in the content of plan in the study will be considered.

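### The planned LLDAS responder rate mixes new attainment with maintenance: patients already in the state at baseline can count, and no baseline LLDAS proportion is shown

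*SAP*

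**What the plan says.** Protocol section 9 lists "achievement of Lupus Low Disease Activity State (LLDAS" among the effectiveness items, next to changes in scores and steroid dose.

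SAP 4.10 opens with a general rule: "A responder is defined as a case where this drug treatment start date and post-treatment assessments are present and the following conditions are met". The SELENA SLEDAI and PGA rules then ask for a fall from baseline (at least 4 points and at least 0.3). The LLDAS rule asks for levels at the assessment:

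- Criterion 1: "SELENA-SLEDAI ≤ 4 and no major active organ involvement", and no haemolytic anaemia or active gastrointestinal lesion reported as an adverse event.
- Criterion 2: "No new signs or symptoms as compared to the last SELENA-SLEDAI assessment".
- Criterion 3: a PGA limit of 1 on the 0–3 scale.
- Criterion 4: "Corticosteroid dose ≤ 7.5 mg/day at time of assessment".
- Criterion 5: the same immunosuppressant as before treatment, and none of the listed unapproved drugs.

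SAP 6.4.2 reports responder rates at Week 24, Week 52 and LOCF. Its one baseline restriction is for a different endpoint: "For steroid dose reduction at Week 40~52, subjects whose baseline average daily steroid dose is > 7.5 mg/day will be included". SAP 6.4.12 plots LLDAS at the same three time points, with the number of patients as denominator. SAP 6.4.2 repeats the LOCF rates by baseline SELENA SLEDAI and baseline steroid dose, among other factors. SAP 6.7 repeats Table 3.021 as Table 5.02 in four classes of starting steroid dose.

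**The concern.** LLDAS is a state, whereas the other responder endpoints in SAP 4.10 require a change. Without a baseline condition or a baseline proportion, the rate cannot show how many patients entered the state on treatment and how many were in it from the start. The protocol describes the item as achievement, and a reader will take the rate in that sense.

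The subgroup tables are more exposed than the overall rate. Patients with low baseline activity and low steroid dose are the ones who can already be in the state. Their LLDAS rate can be higher for that reason alone, and the difference could be read as a predictor of response.

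**Working it through.** Neither document gives an LLDAS rate, a baseline LLDAS share or a sample size based on LLDAS, so there is no planned figure to reproduce. The check has three steps.

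**1. Does an unchanged patient count?** Take a hypothetical patient with the same findings at the start and at Week 52: rash (2) plus low complement (2), so SELENA SLEDAI 4 (weights from Protocol Appendix 1 and SAP 4.11); PGA 0.8; prednisolone 5 mg/day; same immunosuppressant; no listed adverse event or unapproved drug.

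| Rule in SAP 4.10 | Patient | Result |
|---|---|---|
| LLDAS 1: score ≤4, no major organ | 4, skin and immune items only | met |
| LLDAS 2: nothing new since last assessment | unchanged | met |
| LLDAS 3: PGA ≤1 | 0.8 | met |
| LLDAS 4: steroid ≤7.5 mg/day | 5 | met |
| LLDAS 5: same immunosuppressant | unchanged | met |
| SELENA SLEDAI: fall ≥4 | 0 | not met |
| PGA: fall ≥0.3 | 0 | not met |
| Steroid reduction: baseline >7.5 mg/day | 5 | outside the denominator |

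This patient is a responder on LLDAS only.

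**2. Which strata can contain such patients?**

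- Baseline SELENA SLEDAI ≤9 (6.4.2): yes. Baseline 10 or more: no, because criterion 1 fails at baseline. (The second class in 6.4.2 is printed as ≤10; SAP 6.2.1 and 6.3.1 show that 10 or more is meant.)
- Baseline steroid ≤7.5 mg/day (6.4.2): yes. Above 7.5: no, because criterion 4 fails at baseline.
- Table 5.02: everyone in the classes 0 and >0 to ≤5 mg/day meets criterion 4 at baseline. The class >5 to ≤10 straddles the limit. Nobody in the class >10 meets it.

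In each comparison, one side can include patients already in the state and the other cannot, or less so.

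**3. How large could it be?** Let q be the share in the state at baseline, s the share of those in it at the assessment, and r the attainment rate among the others. All three are assumptions.

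Reported rate = q·s + (1−q)·r, so the excess over r is q·(s−r). It is positive whenever s exceeds r.

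Working back from an assumed reported rate of 40%, r = (0.40 − q·s)/(1−q):

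| q | s = 0.70 | s = 0.90 |
|---|---|---|
| 0.05 | 0.365/0.95 = 38.4% | 0.355/0.95 = 37.4% |
| 0.10 | 0.33/0.90 = 36.7% | 0.31/0.90 = 34.4% |
| 0.20 | 0.26/0.80 = 32.5% | 0.22/0.80 = 27.5% |

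Over a wider grid (q 5–30%, s 70–90%, r 20–40%), the excess runs from 0.05 × (0.70 − 0.40) = 1.5 points to 0.30 × (0.90 − 0.20) = 21 points.

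For subgroups, suppose attainment is 30% in both steroid strata and s = 90%. With q = 0 above 7.5 mg/day, that stratum reports 30%. With q = 20% at or below 7.5 mg/day, the other reports 0.20 × 0.90 + 0.80 × 0.30 = 42%. The 12-point gap appears although attainment is equal.

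**The case against.** The proportion of patients in a state at Week 52 is a coherent and legitimate measure in an uncontrolled descriptive survey, and the word achievement does not by itself mean new attainment only. That stands: the definition is not wrong, but the rate needs its baseline counterpart to be interpretable.

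LLDAS is not the SAP's main response measure. The efficacy percentage uses the SELENA SLEDAI responder, which the unchanged patient above cannot meet, and no sample size rests on LLDAS. This limits the consequence.

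The strata identified in step 2 already give attainment rates free of the problem. This also stands, but they correct neither the overall rate nor the comparison with the milder strata.

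A reader might infer that the SAP expects many patients in LLDAS at entry, because it has low baseline classes for PGA and steroid dose and a low class in the table described as "SELENA SLEDAI score by presence/absence of prior treatment for SLE". The documents do not support that. Those classes partition whole scales, one variable at a time; a listed class need not be populated, and LLDAS needs all criteria together. The labelled indication quoted in Protocol section 3 also calls for disease activity despite treatment. That should reduce the number affected, although no score threshold is set and the survey takes all treated patients aside from the paediatric exception.

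SAP 5.4 and 6.6 are blacked out and the table mocks are separate files, so a baseline LLDAS analysis elsewhere cannot be excluded. None appears in the visible definition or responder analyses.

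**Conclusion.** The point holds as a property of the definition and the denominator. The overall LLDAS rate mixes attainment with maintenance, and the comparisons by baseline steroid dose and SELENA SLEDAI favour milder groups partly by construction.

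The size is unknown. The figures above rest on assumed values of q, s and r, and at a 5% baseline share with a reported 40% the shift is only 1.6 to 2.6 points (40 − 38.4 and 40 − 37.4).

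Two stronger readings should not be drawn. One is that the planned rate is materially inflated: nothing in the documents shows how many patients were in the state at baseline. The other is that such patients have nothing to achieve: they must still avoid new activity and stay on the same immunosuppressant to count. This is a defect of interpretability in a descriptive effectiveness item, and it can be repaired with data already collected.

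**What to change.** 1. Keep the all-patient rate for comparability with earlier outputs, labelled 'in LLDAS at assessment'.
2. In SAP 4.10, derive a baseline flag from what can be evaluated then: SELENA SLEDAI ≤4 with no major organ activity on that index, PGA ≤1, and average daily steroid dose ≤7.5 mg/day by the baseline rule in SAP 4.12. Add an 'unknown' class for missing data.
3. State that the flag approximates LLDAS. Criteria 2 and 5 compare with an earlier point, and the adverse-event part of criterion 1 uses events collected only after the start of administration (Protocol section 8, item 16). None of these can be evaluated at baseline, so the flag is looser than the endpoint.
4. Add to Tables 3.021, 3.022, 5.02 and 10.2 and the LLDAS figure: the baseline proportion, the attainment rate among patients not flagged, and the maintenance rate among those flagged.
5. Base any statement on achievement of LLDAS, and any subgroup comparison, on the attainment rate.
6. Date the addition in the SAP change history, since the protocol gives July 2025 for completion of the final analysis.

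The cost is one derived variable and a few extra table rows, with no new data. The attainment rate will have a smaller denominator and is likely to be somewhat less favourable than the all-patient rate.
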